The fibre-optic sensor system consists of a sensor mat, an interrogator and a personal computer (PC), and records respiratory and BCG signals in patients during MRI. The metal-free sensor mat is placed under the patient's back, does not pose a threat to the patient and has no influence over the quality of imaging. The interrogation module detects the optical signal including vital signs, and the PC with software developed for signal processing and visualisation enable the MRI operator to monitor patient's RR and HR.

Up to 200 MRI patients in different age, weight and gender groups will be participated in the study. They will be asked to complete the State Trait Anxiety Inventory (STAI) questionnaire in order to estimate anxiety level before and after the MRI scanning. Relations between the STAI X-1 scores and the mean RR and/or HR values recorded at the beginning and the end of the MRI scanning will be analysed using descriptive statistic methods. Finally, the values of the physiological parameters, which may indicate a dangerous level of anxiety will be determined. Positive results of the clinical evaluation will predestine the fibre-optic sensor system to be implemented in routine MRI procedures.

General information

Protocol Title

Clinical evaluation of a fibre-optic sensor system for monitoring respiration activity and heart work during MRI examinations

Short title

Evaluation of an MRI-compatible vital signs sensor system

Acronym

OPTO-MRI

Sponsor

Military Institute of Aviation Medicine (MIAM)
[name]
[name]
Poland

Primary Investigator (PI)

[name], D.Sc., Ph. D.
[name]
[name]
Poland
[contact]
email: [contact]

Other medical and/or technical institutions involved in the research

No other co-operators

Rationale & background information

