Conventional monitoring equipment is not designed to work in the harsh MRI environment, distinguished by a magnetic induction of 1.5 T, 3.0 T, or even higher values and with radio frequency (RF) impulses of considerable electromagnetic (EM) field intensity [13]. The presence of metal or electronic components under such conditions can cause burns on the patient's skin and alter the EM field distribution and, thus, degrade the quality of imaging. Additionally, the signal transmitted using electrical conductive wires is vulnerable to the effects of a strong EM field, which complements the list of drawbacks of typical electronic measuring devices. On the other hand, optical sensors are fully penetrable in terms of the EM radiation applied in MRI, causing no interference. They are free from metal parts and function via optical fibres, resulting in their immunity to EM fields.

Study goals and objectives

The main objectives include:

1. Testing the sensor system with participation of MRI patients, where the result measures relate both to feasibility and health outcomes.
2. Verifying the signal quality, detecting RR and HR, and checking long-term measurement capabilities of the sensor system.
3. Analysing changes in RR and HR in the context of the system ability to detect a high level of stress, hyperventilation and other symptoms of claustrophobia in MRI patients.

Study Design

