MIAM is both a research institute and medical centre, where data management and information security are provided in accordance with the ISO IEC 27001 standard. A copy of the certificate is included as **Appendix A**.

Statistical Analysis Plan

Descriptive statistic methods will be used to evaluate the state anxiety and RR and/or HR indicators, as well as to assess the difference between the first and second anxiety measurement. A correlation analysis with the Pearson product-moment correlation coefficient will be performed to check if the initial RR and/or HR level is related to state anxiety measured right before the MRI study.

Since we hypothesise about the individual variability of the change in the RR and/or HR levels during an MRI session, a growth mixture model analysis [22] will be performed to statistically differentiate the subject groups according to the trends in repeated measures of RR and/or HR. After that, the analysis will be performed with the use of the Student's t-test to check whether the so-identified groups differ on the magnitude of change in the state anxiety observed during the study. An Alpha level of 0.05 will be used in all of the statistical tests.

The analysis will be performed using R statistical software version 3.4.0 [23]. The Growth mixture model analysis will be performed using the lcmm package version 1.7.7 [24]. The power analysis will be performed with the pwr package version 1.2-1 [25]. Plots will be created using the ggplot2 package version 2.2.1 [26].

Quality Assurance

MIAM has a quality management certificate based on the ISO 9001:2008 and AQAP 2120:2009 requirements. Copies of the certificates are included as **Appendix B**.

Expected Outcomes of the Study

Correlations between the STAI X-1 scores collected before and after the MRI scanning and the mean RR values recorded at the beginning and the end of the MRI scanning, respectively, are expected. Similarly, correlations between the STAI X-1 scores and the HR indicators should also be noticeable. We also expect the STAI X-2 scores will be useful in estimating the risk of anxiety symptoms during MRI.

At least two manuscripts, one containing the results of the STAI scores in relation to RR, and the other containing the results of the STAI and HR analysis, will be submitted for publication.

Dissemination of Results and Publication Policy

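### Does testing everything at 0.05, with no primary test and no multiplicity control, undermine the anxiety conclusions?

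*Combined protocol and SAP*

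**What the plan says.** The Statistical Analysis Plan section describes two inferential analyses, each worded for RR and/or HR.

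- A Pearson correlation, "to check if the initial RR and/or HR level is related to state anxiety measured right before the MRI study".
- A Student's t-test on groups found by a growth mixture model, to "check whether the so-identified groups differ on the magnitude of change in the state anxiety observed during the study".

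The significance level is set once: "An Alpha level of 0.05 will be used in all of the statistical tests". No section ranks the tests, orders them, adjusts for their number or calls them exploratory.

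Other sections bear on how many tests there are and what they are for.

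- The third item under Study goals and objectives names both signals: "Analysing changes in RR and HR in the context of the system ability to detect a high level of stress".
- Expected Outcomes of the Study plans at least two papers, "one containing the results of the STAI scores in relation to RR, and the other containing the results of the STAI and HR analysis". It also predicts correlations at the end of the scan.
- The Project summary says that the relations between anxiety scores and the mean values "recorded at the beginning and the end of the MRI scanning will be analysed using descriptive statistic methods". It continues: "Finally, the values of the physiological parameters, which may indicate a dangerous level of anxiety will be determined". It closes with: "Positive results of the clinical evaluation will predestine the fibre-optic sensor system to be implemented in routine MRI procedures".
- Study Design calls the study observational and sets a maximum of 200 patients.

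**The concern.** Several tests, each at 0.05, give more than a 5% chance that at least one is significant when nothing is there. Because RR and/or HR is left open, an analyst could also dwell on whichever signal worked. The summary goes on to plan RR and HR values that mark dangerous anxiety, which presumes a real link, and it ties an undefined positive outcome to routine use. If one chance finding were taken as proof that the mat detects anxiety, a monitoring threshold could rest on noise. The natural remedy would be to name a primary test or to control the error rate across the family.

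**Working it through.** The plan states no study-wide error rate and no power, so there is no figure of its own to reproduce. The only stated error rate is 0.05 per test.

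**Inputs from the documents.** Alpha is 0.05 per test. There are two tests per signal if the mixture model gives two groups, one or two signals, and at most 200 patients.

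**Inputs assumed, because the documents give none.** Two groups per signal, a separate mixture model for each signal, and the correlations between RR and HR, between start and end of scan, and between the two anxiety scores.

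**Chance of at least one false positive with no true link.** For k independent tests this is 1 − 0.95^k. Under any dependence it is at most 0.05k.

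| Tests counted | k | 1 − 0.95^k | Upper bound |
|---|---|---|---|
| One signal, both tests | 2 | 9.75% | 10% |
| Both signals, one shared grouping | 3 | 14.3% | 15% |
| Both signals, separate groupings | 4 | 18.5% | 20% |
| As above, plus end-of-scan correlations | 6 | 26.5% | 30% |

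**Effect of dependence.** Null data were simulated for 200 patients with RR–HR correlations from 0 to 0.8. A threshold split stood in for the mixture classes. One signal gave about 9% to 10%, and four tests gave about 15% to 19%, lowest when RR and HR were most alike.

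**Effect of the number of groups.** The plan does not fix this number. With one group per signal the t-tests vanish, and the two initial correlations give 8% to 10%. With three groups per signal (assumed split 25/50/25) and all pairwise t-tests, simulation gave about 17% for one signal and 31% for both. So 18.5% belongs to one scenario and is not a ceiling.

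**Effect of the decision rule.** These rates matter only if any single significant result counts as success. Expected Outcomes anticipates correlations for RR and for HR. If both initial correlations had to be significant, the false positive chance would be 0.05 × 0.05 = 0.25% under independence, and about 0.4% to 0.5% with an assumed RR–HR correlation of 0.3. The plan states neither rule.

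**What each remedy would do.**

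- Naming one primary test, or labelling the tests exploratory, leaves every estimate, interval and p-value as it is. Only the description changes.
- Holm across four tests starts at 0.05 / 4 = 0.0125. At that step, for a correlation:

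| Patients | Detectable r, 80% power: 0.05 → 0.0125 | Power at r = 0.25: 0.05 → 0.0125 |
|---|---|---|
| 200 | 0.197 → 0.233 | 95% → 86% |
| 150 (assumed, since 200 is a maximum) | 0.226 → 0.268 | 87% → 73% |

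Holm across four tests is also not fully defined until someone says which comparison is used when a model returns three or more groups.

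**The case for a change.** The best case for a change is that the plan never calls these tests exploratory. The summary's descriptive wording covers the relations at the beginning and end of the scan but not the group t-tests, and a significance level is set for them all. The third objective and the two planned papers show that both signals will be examined. The summary looks beyond description, to danger values and routine use. One sentence would settle the matter at no cost in power to the chosen test.

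Much of this stands. The absence is real, the error rates are right, and a sentence on status would be tidy. The status of the end-of-scan correlations is also unclear, since the summary treats them descriptively and Expected Outcomes predicts them.

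The consequence does not follow. The summary's closing statement concerns the evaluation of the whole device, and the objectives include feasibility, signal quality and long-term measurement. Nothing ties routine use to any one p-value. The two tests ask different questions: initial level against anxiety before the scan, and course during the scan against change in anxiety. With a separate paper for each signal, treating each signal as its own family, at about 10%, is defensible. Pooling them into one family of four is a reader's choice.

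**Conclusion.** No change is needed. With no true link and two groups per signal, the chance of at least one nominally significant result is about 10% per signal and about 15% to 19% for both signals pooled, with a strict bound of 20% for four tests. These figures depend on the number of groups, on pooling the signals, and on assumed correlations.

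They describe how cautiously a lone significant result should be read. They do not contradict any error rate the plan claims. In an observational device evaluation, analysts can fill the gap sensibly by reporting all the planned tests with estimates and confidence intervals and by not resting a detection claim on one isolated result. Formal control across signals is a trade-off on which reasonable statisticians differ, and here it would give up 9 percentage points of power at 200 patients (95 − 86), or 14 at 150 (87 − 73), for r = 0.25. The judgement would differ if the plan made one joint anxiety-detection claim that any single significant test could satisfy. It does not.

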Appendix A

(Copy of ISO/IEC 27001:2013 certificate)

Appendix B

(Copies of ISO 9001:2008 and AQAP 2120:2009 certificates)
